2.2 Secondary Objectives

- To determine median rPFS
- To determine radiologic response rate
- To determine OS
- To determine safety and tolerability

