5.6 End of Treatment Evaluation or Unscheduled/Early Termination Visit

Procedures listed in the study schedule will be conducted 30 days (+7 days) after the last dose of study drug or in the event of premature study termination.

The End of Treatment procedures listed in the study schedule will also be performed at the time of progression or initiation of another treatment if the subject discontinued study treatment for other reasons.

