5.7 Long-Term Follow-Up

After completing the end of treatment evaluation, follow-up continues for subjects who have not progressed with assessments including PSA, bone scan and/or CT scans performed every 3 months or per standard of care for up to 2 years from initiation of study therapy or until progression of disease or initiation of other treatment. Modalities of disease assessment at baseline will be used at subsequent response evaluations for determination of response and/or disease progression.

Adverse events and concomitant medications reported at any follow-up visits will include outcome of any ongoing unresolved events, new events attributed to the study treatment, deaths, hospitalizations, and infectious episodes requiring prescription or IV anti-infectives or GI toxicity. Follow-up for treatment related toxicities which may include physical exam, CBC and chemistries will be required till resolution or stabilization of the toxicity.

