8.4.3 Efficacy Analysis

The Efficacy Analysis Set will consist of all subjects who receive at least 1 dose of Sacituzumab Govitecan and have at least 1 post-dose assessment of PSA; and/or 1 post-dose radiographic assessment for subjects with evaluable and/or measurable metastases at screening, 1 post-dose assessment of metastatic disease will be required. Subjects who

discontinue study participation early so they do not meet criteria for inclusion in the efficacy analysis set can be replaced.

Changes in PSA will be compared to baseline and maximal change from baseline and change at Week 9 (e.g., end of Cycle 3) will also be determined, as will duration of response. Maximum change in soft tissue lesions as seen on CT or MRI of the chest, abdomen and pelvis, as well as changes on bone scintigraphy according to the PCWG2 criteria will also be compared to baseline, and summarized.

A subgroup efficacy analysis will be conducted in the group of patients who continued single agent ARSI in combination with Sacituzumab Govitecan.

Definition and analysis of primary efficacy endpoint:

PSA response rate: Subjects who achieve $\geq 50\%$ PSA decline at or before 9 weeks of therapy with Sacituzumab Govitecan are considered to have responded. PSA responses will be analyzed by descriptive statistics and summarized in tabular format (frequency tables). The overall PSA response rate will be reported along with the corresponding 95% confidence interval which will be constructed using the Wilson score method.

6-month rPFS rate: Proportion of subjects remaining alive and progression free (using PCWG2 criteria) 6 months from time of starting treatment as estimated by the Kaplan-Meier method. The point estimate of the 6-month rPFS rate will be reported along with the corresponding two-sided 95% confidence interval.

Definition and analysis of secondary efficacy endpoints:

- i. *Median rPFS.* The probability distribution of PFS will be estimated using the Kaplan-Meier method. The median will be estimated from this distribution. Subjects who have not died or progressed (using PCWG2 criteria) will be censored at the date of last assessment.
- ii. *Median OS.* OS is the duration from start of treatment until death from any cause. The probability distribution of OS will be estimated using the Kaplan-Meier method. The median will be estimated from this distribution. Subjects who have not died will be censored at the date of last contact.

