APPENDIX B: STUDY CALENDAR

	Screening	Cycle 1		Cycle 2		Cycle 3			Cycle 4+		End of Treatment /Progression	Follow-up ⁷
	Within 30 days prior to C1D1	Day 1 (±3)	Day 8 (±3)	Day 1 (±3)	Day 8 (±3)	Day 1 (±3)	Day 8 (±3)	Day 15 (±7)	Day 1 (±3)	Day 8 (±3)	30 days from last treatment (+7)	Every 3 months (±7)
Assessments												
Medical History & Comorbidities	X	X		X		X			X			
Consent	X											
Physical exam and ECOG PS	X	X		X		X			X		X	
Toxicity assessment		X	X	X	X	X	X		X	X	X	
Concomitant medications	X	X	X	X	X	X	X		X	X	X	
Vital signs, height, weight ¹	X	X	X	X	X	X	X		X	X	X	
ECG	X										X	
Laboratory Evaluations												
PSA	X	X	X	X		X			X		X	X
Testosterone	X											
CTCs & plasma	X	X	X	X		X			X ²		X	
Buffy coat	X											
CBC with differential ⁹	X	X	X	X	X	X	X		X	X	X	
CMP ³	X	X	X	X	X	X	X		X	X	X	
PT/INR and PTT	X						X					
Urinalysis ⁴	X											
Treatment-Experimental Interventions												
Sacituzumab Govitecan		X	X	X	X	X	X		X	X		

Metastatic Biopsy ⁵	X							X				
Imaging studies												
^{99m} Tc-MDP bone scan ⁶	X							X ²		X ⁸		X
CT Chest; CT or MRI Abdomen/Pelvis ⁶	X							X ²		X ⁸		X

¹Height is only required during screening. BP and pulse prior to first infusion, every 15 for the first hour and then every 30 minutes until completing IV administration, at completion, and then additionally 30 minutes later. In absence of significant changes, frequency may be reduced with subsequent doses to prior to infusion, at 30 minutes, and then at completion. All time points may be collected \pm 5 minutes.

²Every 3 cycles (cycle 7, cycle 10, etc.) or every 9 weeks; if a cycle is delayed, procedures should still be performed every 9 weeks.

³Sodium, potassium, chloride, bicarbonate, BUN, glucose, creatinine, AST, ALT, alkaline phosphatase, lactate dehydrogenase, total bilirubin, total protein, albumin, serum calcium, magnesium, and phosphorous

⁴To include pH, specific gravity and hemoglobin, glucose, ketones, and protein by dipstick, with microscopic exam if any of the dipstick analytes are 2+ or higher.

⁵Fresh or Archived tumor from standard of care biopsy from metastatic site required for enrollment. On study biopsy at cycle 3 day 15 should be performed, regardless of treatment delays, to be performed in line with CT and bone scans.

⁶Window extended to \pm 10 days for scans.

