⁷All subjects should have adverse events evaluated at least 30 days from the last dose of study drug. Follow-up for progression will be performed every 3 months or per standard of care for up to 2 years from initiation of study therapy if subjects discontinue study treatment prior to progression. For subjects coming off-treatment due to progression, follow-up is complete once AEs have been evaluated at least 30 days after the last dose of the study drug.

⁸If not performed within 30 days of End of Treatment/Progression

⁹If lab values are not within normal range on day 1 or day 8, consider repeat CBC with differential on day 15, as per MD discretion. In the case of a Grade 3 ANC subjects should be assessed weekly and for grade 4 ANC subjects should be assessed bi-weekly as per section 6.4.1.

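### Overall survival is a secondary objective with a Kaplan-Meier median, but scheduled contact ends at progression, so later deaths are captured only by chance and the censoring is likely informative.

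*Combined protocol and SAP*

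**What the plan says.** Section 2.2 lists among the secondary objectives "To determine OS". Section 8.4.3 measures OS from start of treatment to death from any cause, estimates the median by Kaplan-Meier, and adds: "Subjects who have not died will be censored at the date of last contact". It does not say whether contact outside the study counts.

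Contact after treatment is set in three places.

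- **Section 5.7:** "follow-up continues for subjects who have not progressed", for up to 2 years, "or until progression of disease or initiation of other treatment". Deaths are among the events recorded at these visits.
- **Appendix B, footnote 7:** for subjects who stop treatment before progression, "Follow-up for progression will be performed every 3 months or per standard of care for up to 2 years from initiation of study therapy". For subjects who stop because of progression, "For subjects coming off-treatment due to progression, follow-up is complete once AEs have been evaluated at least 30 days after the last dose".
- **Section 5.6:** the End of Treatment procedures "will also be performed at the time of progression or initiation of another treatment if the subject discontinued study treatment for other reasons". This is a single repeat.

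The calendar's Follow-up column marks PSA, bone scan and CT or MRI, and nothing for survival status.

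**The concern.** Death from any cause can occur long after progression, and in this population most deaths would be expected then. The plan stops scheduled contact at that point. Kaplan-Meier estimation assumes that subjects censored at a given time have the same later risk of death as those still followed. Here censoring is triggered by progression, which plausibly raises that risk, so the assumption is doubtful.

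The direction of the error depends on undocumented site practice. If late deaths are simply missed, OS is overestimated or its median is not reached; a downward bias in that case would need a higher death hazard before progression than after it. If sites enter the deaths they hear of but leave other subjects censored at the last study visit, the error shrinks and can turn negative.

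There is also an inconsistency. For subjects who stop treatment before progression, section 5.7 ends follow-up when other treatment starts, while footnote 7 follows them for up to 2 years without that stop. In addition, the section 5.7 stop is not limited to radiographic progression, so it could end scans before a radiographic event. The figures below concern OS only.

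**Working it through.** **1. Can another route capture a late death?**

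| Section | Provision | Captures deaths after progression? |
|---|---|---|
| 5.7 | Deaths recorded at follow-up visits | No: progressed subjects have no such visits |
| 7.2 | AEs for 30 days after last dose; later, only drug-related SAEs the investigator learns of | Passive, related events only |
| 7.3 | AE period ends at the last scheduled evaluation, or when drug-related toxicities and ongoing SAEs have resolved, if later | Not systematic |
| 7.1.4 | Death is an SAE criterion, but progression of the underlying disease is not an SAE | Not for disease progression itself |
| 7.5 | SAEs and possibly related events followed to resolution or stability | Only where such an event is open |

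No section schedules survival contact after progression.

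**2. Inputs for an illustration.** The plan gives no expected OS median, death count or precision, so it has no OS figure to reproduce.

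- From the plan: 6-month rPFS of 20% or 40%, 55 enrolled or 45 evaluable (section 8.3); 24 months (section 5.7).
- Assumed: constant hazards; a share d = 5, 10 or 20% of rPFS events are deaths; post-progression death hazard h = 0.03, 0.06 or 0.10 per month; last contact L = 1 or 3 months after progression.

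This makes 2 × 3 × 3 × 2 = 36 scenarios. The total rPFS hazard H is -ln(0.20)/6 = 0.268 or -ln(0.40)/6 = 0.153 per month. The four scenarios with d = 20% and h = 0.03 are set aside, because the death hazard before progression (0.20 × 0.268 = 0.054, or 0.20 × 0.153 = 0.031) exceeds h. The other 32 have a higher death hazard after progression than before.

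**3. One scenario by hand** (rPFS 40%, d = 10%, h = 0.06, L = 1, no late deaths learned of).

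True 12-month OS, with g = H(1 - d) = 0.9 × 0.1527 = 0.1374:

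exp(-12H) + g[exp(-12h) - exp(-12H)]/(H - h) = 0.160 + 0.1374 × (0.487 - 0.160)/0.0927 = 0.64.

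Kaplan-Meier sees only subjects who are progression-free or progressed within the last L months. After month 1 the ratio of the second group to the first is

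R = g[exp((H - h)L) - 1]/(H - h) = 0.1374 × 0.0972/0.0927 = 0.144.

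The observed death hazard is (dH + hR)/(1 + R) = (0.0153 + 0.0086)/1.144 = 0.0209 per month. In month 1 it rises from 0.0153 to this value, averaging about 0.018. The Kaplan-Meier estimate at 12 months tends to exp[-(0.018 + 11 × 0.0209)] = 0.78.

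The plan would thus report about 78% against a true 64%. Simulation of 10,000 trials gave the same 0.78, with 8.2 of 36.4 deaths captured and the median not reached in 76% of trials, against 0.9% with full collection. If sites learn of 25% or 50% of late deaths, the estimate becomes 0.70 or 0.64.

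**4. All 32 scenarios** (simulation, 55 subjects).

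| Late deaths learned of | Deaths captured | Error in 12-month OS, points |
|---|---|---|
| None | 15-48% (middle 31%); 4-22 of 24-49 | +0.7 to +25 (middle 8) |
| 25% | 36-61% | -8 to +12 |
| 50% | 57-74% | -12 to +5; negative in 23 of 32 |

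With none learned of, only 3-13 subjects are still followed at 12 months. As a check for L = 1, subjects progression-free at 11 months number 55 × exp(-0.268 × 11), about 3, and 55 × exp(-0.153 × 11), about 10.

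For the median:

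- **h = 0.06 to 0.10, none learned of:** not reached in 6-89% of trials with 55 subjects (8-88% with 45), against at most 1.6% (2.3%) with full collection to 24 months.
- **h = 0.03, none learned of:** not reached in 73-94%, and in 46-85% even with full collection.
- **h = 0.03, 50% learned of:** a median is reported in 94-100% of trials, although full collection would reach one in only 15-54%.

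**The case against.** The strongest reply is that last contact in section 8.4.3 need not mean a study visit. Sites may update vital status from the chart for survivors as well as for deaths. If status to 24 months is known for a random 50% of subjects, the 12-month error in the same 32 scenarios is +0.2 to +7.2 points (middle 2.3); at 75% it is about 0 to +3 (middle 1). These shares are also assumed. The point has force: 25 points is the upper end of the case with no late information. But the plan does not require such updating, some error usually remains, and updating survivors is what the fix asks for.

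Other points are fair but do not remove the gap.

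- Section 5.7 does collect deaths before progression, so the gap is confined to the time after progression, new treatment or the 2-year limit.
- Treatment past progression with approval (section 5.8), or an unresolved toxicity, can prolong contact for some subjects, but not systematically.
- The sign in the no-information case is partly built in: the four scenarios set aside are the only ones with a negative error (-7.7, -3.8, -0.3 and -0.2 points). That is why the conclusion is conditional on a higher death risk after progression.
- Footnote 7 could be read as silent on new treatment and not as contradicting section 5.7. Either way, two sites could follow the same subject differently.
- OS has no hypothesis, power or decision rule in this single-arm trial. This limits the severity but does not make the estimate interpretable.

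**Conclusion.** The concern holds. The plan's own rules end scheduled contact at progression for an endpoint defined by death from any cause, and no section restores it. That conclusion rests on the text alone.

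The size depends on assumptions about hazards and site practice. If death risk is higher after progression and no late deaths are learned of, 12-month OS is too high by 0.7 to 25 points. With partial passive capture and other subjects left at last study contact, the sign can reverse. The model ends contact after an rPFS event; PSA or clinical progression, or new treatment, could end it sooner, and treatment past progression could delay it.

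The effect is on one descriptive secondary endpoint. It should be fixed, and early, because some subjects who have left follow-up may not be reachable later.

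**What to change.** - Amend section 5.7, footnote 7 and the calendar to collect survival status (alive or dead, with date) by phone or chart review every 3 months for all treated subjects, regardless of progression or new treatment, until death, withdrawal of consent or 2 years from first dose.
- Include a status check, where consent permits, for subjects who have already left follow-up.
- Reconcile section 5.7 with footnote 7 on whether follow-up for progression ends when other treatment starts.
- In section 8.4.3, define last contact as the last date known alive, so that survivors are updated as well as deaths. Report survival at fixed times, for example 12 months, if the median is not reached.
- Otherwise, remove OS from section 2.2 and median OS from section 8.4.3, and report only deaths observed on study.

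The cost is a protocol amendment, modest site, data-entry and monitoring work (one status check per progressed subject every 3 months, with no visit or scan), and possibly a consent update for enrolled subjects. Some subjects may not be reachable. If survival after progression is long, a 2-year limit may still not reach the median, which is why fixed-time survival is included.

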APPENDIX C: ELEMENTS OF INFORMED CONSENT

Signed studies items: informed consent will be obtained from all subjects participating in clinical research or the subject's legally authorized representative. This consent must include the following:

- A statement that the study involves research and an explanation of the purposes of the research; a description of the procedures to be followed and identification of any procedures that are experimental; and the expected duration of the subject's participation.
- A description of any reasonably foreseeable risks or discomforts to the subject.
- A description of any benefits to the subject or to others that may reasonably be expected from the research. If the subject is to be paid for participating in the study, the consent form must state the amount he/she will receive and the schedule of payment (to assure neither coercion nor undue influence).
- A disclosure of appropriate alternative procedures or courses of treatment, if any, that might be advantageous to the subject.
- A statement describing the extent, if any, to which confidentiality of records identifying the subject will be maintained and noting the possibility that regulatory agencies, the IRB, or an authorized contract research organization (CRO) may inspect the records.
- For research involving more than minimal risk, an explanation of whether any medical treatment is available if injury occurs and, if so, what it consists of, or where further information may be obtained.
- An explanation of whom to contact, including the appropriate telephone number, for answers to pertinent questions about the research and research subject's rights, and whom to contact in the event of a research-related injury to the subject. (NOTE: In some cases it may be necessary to identify some person other than the investigator as the contact. The guidance of the IRB may be required.)
- A statement that participation is voluntary, that refusal to participate will involve no penalty or loss of benefits to which the subject is otherwise entitled, and that the subject
- A copy of the consent form given to the subject.
- A statement of consent, e.g. "I agree to participate."
- A place for signature and date of signature for the research subject.
- A statement that the particular treatment or procedures may involve risks to the subject (or to the embryo or fetus, if the subject is or may become pregnant) that are currently unforeseeable.
- Anticipated circumstances under which the subject's participation may be terminated by the investigator without regard to the subject's consent.
- Any additional costs to the subject that may result from participation in the research.
- The consequences of a subject's decision to withdraw from the research and procedures for orderly termination of participation by the subject.
- A statement that significant new findings developed during the course of the research that may relate to the subject's willingness to continue participation will be provided to the subject.
- The approximate number of subjects involved in the study.

APPENDIX D: THE DECLARATION OF HELSINKI

WORLD MEDICAL ASSOCIATION DECLARATION OF HELSINKI Ethical Principles for Medical Research Involving Human Patients

Adopted by the 18th WMA General Assembly, Helsinki, Finland, June 1964, and amended by the:

29th WMA General Assembly, Tokyo, Japan, October 1975, 35th WMA General Assembly, Venice, Italy, October 1983, 41st WMA General Assembly, Hong Kong, September 198948th WMA General Assembly, Somerset West, Republic of South Africa, October 1996 52nd WMA General Assembly, Edinburgh, Scotland, October 2000

53rd WMA General Assembly, Washington 2002 (Note of Clarification on paragraph 29 added) 55th WMA General Assembly, Tokyo 2004 (Note of Clarification on Paragraph 30 added) 59th WMA General Assembly, Seoul, October 2008

A. INTRODUCTION

1. The World Medical Association (WMA) has developed the Declaration of Helsinki as a statement of ethical principles for medical research involving human patients, including research on identifiable human material and data. The Declaration is intended to be read as a whole and each of its constituent paragraphs should not be applied without consideration of all other relevant paragraphs.
2. Although the Declaration is addressed primarily to physicians, the WMA encourages other participants in medical research involving human patients to adopt these principles.
3. It is the duty of the physician to promote and safeguard the health of patients, including those who are involved in medical research. The physician's knowledge and conscience are dedicated to the fulfillment of this duty.
4. The Declaration of Geneva of the WMA binds the physician with the words, "The health of my patient will be my first consideration," and the International Code of Medical Ethics declares that, "A physician shall act in the patient's best interest when providing medical care."
5. Medical progress is based on research that ultimately must include studies involving human patients. Populations that are underrepresented in medical research should be provided appropriate access to participation in research.
6. In medical research involving human patients, the well-being of the individual research patient must take precedence over all other interests.
7. The primary purpose of medical research involving human patients is to understand the causes, development and effects of diseases and improve preventive, diagnostic and therapeutic interventions (methods, procedures and treatments). Even the best current interventions must be evaluated continually through research for their safety, effectiveness, efficiency, accessibility and quality.
8. In medical practice and in medical research, most interventions involve risks and burdens.
9. Medical research is patient to ethical standards that promote respect for all human patients and protect their health and rights. Some research populations are particularly vulnerable and need special protection. These include those who cannot give or refuse consent for themselves and those who may be vulnerable to coercion or undue influence.

10. Physicians should consider the ethical, legal and regulatory norms and standards for research involving human patients in their own countries as well as applicable international norms and standards. No national or international ethical, legal or regulatory requirement should reduce or eliminate any of the protections for research patients set forth in this Declaration.

B. BASIC PRINCIPLES FOR ALL MEDICAL RESEARCH

1. It is the duty of physicians who participate in medical research to protect the life, health, dignity, integrity, right to self-determination, privacy, and confidentiality of personal information of research patients.
2. Medical research involving human patients must conform to generally accepted scientific principles, be based on a thorough knowledge of the scientific literature, other relevant sources of information, and adequate laboratory and, as appropriate, animal experimentation. The welfare of animals used for research must be respected.
3. Appropriate caution must be exercised in the conduct of medical research that may harm the environment.
4. The design and performance of each research study involving human patients must be clearly described in a research protocol. The protocol should contain a statement of the ethical considerations involved and should indicate how the principles in this Declaration have been addressed. The protocol should include information regarding funding, sponsors, institutional affiliations, other potential conflicts of interest, incentives for patients and provisions for treating and/or compensating patients who are harmed as a consequence of participation in the research study. The protocol should describe arrangements for post-study access by study patients to interventions identified as beneficial in the study or access to other appropriate care or benefits.
5. The research protocol must be submitted for consideration, comment, guidance and approval to a research ethics committee before the study begins. This committee must be independent of the researcher, the sponsor and any other undue influence. It must take into consideration the laws and regulations of the country or countries in which the research is to be performed as well as applicable international norms and standards but these must not be allowed to reduce or eliminate any of the protections for research patients set forth in this Declaration. The committee must have the right to monitor ongoing studies. The researcher must provide monitoring information to the committee, especially information about any SAEs. No change to the protocol may be made without consideration and approval by the committee.
6. Medical research involving human patients must be conducted only by individuals with the appropriate scientific training and qualifications. Research on patients or healthy volunteers requires the supervision of a competent and appropriately qualified physician or other health care professional. The responsibility for the protection of research patients must always rest with the physician or other health care professional and never the research patients, even though they have given consent.
7. Medical research involving a disadvantaged or vulnerable population or community is only justified if the research is responsive to the health needs and priorities of this population or community and if there is a reasonable likelihood that this population or community stands to benefit from the results of the research.
8. Every medical research study involving human patients must be preceded by careful assessment of predictable risks and burdens to the individuals and communities involved in the research in comparison with foreseeable benefits to them and to other individuals or communities affected by the condition under investigation.

9. Every clinical study must be registered in a publicly accessible database before recruitment of the first patient.
10. Physicians may not participate in a research study involving human patients unless they are confident that the risks involved have been adequately assessed and can be satisfactorily managed. Physicians must immediately stop a study when the risks are found to outweigh the potential benefits or when there is conclusive proof of positive and beneficial results.
11. Medical research involving human patients may only be conducted if the importance of the objective outweighs the inherent risks and burdens to the research patients.
12. Participation by competent individuals as patients in medical research must be voluntary. Although it may be appropriate to consult family members or community leaders, no competent individual may be enrolled in a research study unless he or she freely agrees.
13. Every precaution must be taken to protect the privacy of research patients and the confidentiality of their personal information and to minimize the impact of the study on their physical, mental and social integrity.
14. In medical research involving competent human patients, each potential patient must be adequately informed of the aims, methods, sources of funding, any possible conflicts of interest, institutional affiliations of the researcher, the anticipated benefits and potential risks of the study and the discomfort it may entail, and any other relevant aspects of the study. The potential patient must be informed of the right to refuse to participate in the study or to withdraw consent to participate at any time without reprisal. Special attention should be given to the specific information needs of individual potential patients as well as to the methods used to deliver the information. After ensuring that the potential patient has understood the information, the physician or another appropriately qualified individual must then seek the potential patient's freely-given informed consent, preferably in writing. If the consent cannot be expressed in writing, the non-written consent must be formally documented and witnessed.
15. For medical research using identifiable human material or data, physicians must normally seek consent for the collection, analysis, storage and/or reuse. There may be situations where consent would be impossible or impractical to obtain for such research or would pose a threat to the validity of the research. In such situations the research may be done only after consideration and approval of a research ethics committee.
16. When seeking informed consent for participation in a research study the physician should be particularly cautious if the potential patient is in a dependent relationship with the physician or may consent under duress. In such situations the informed consent should be sought by an appropriately qualified individual who is completely independent of this relationship.
17. For a potential research patient who is incompetent, the physician must seek informed consent from the legally authorized representative. These individuals must not be included in a research study that has no likelihood of benefit for them unless it is intended to promote the health of the population represented by the potential patient, the research cannot instead be performed with competent persons, and the research entails only minimal risk and minimal burden.
18. When a potential research patient who is deemed incompetent is able to give assent to decisions about participation in research, the physician must seek that assent in addition to the consent of the legally authorized representative. The potential patient's dissent should be respected.
19. Research involving patients who are physically or mentally incapable of giving consent, for example, unconscious patients, may be done only if the physical or mental condition that prevents giving informed consent is a necessary characteristic of the research population. In such circumstances the physician should seek informed consent from the legally authorized representative. If no such representative is available and if the research cannot be delayed, the

study may proceed without informed consent provided that the specific reasons for involving patients with a condition that renders them unable to give informed consent have been stated in the research protocol and the study has been approved by a research ethics committee. Consent to remain in the research should be obtained as soon as possible from the patient or a legally authorized representative.

20. Authors, editors and publishers all have ethical obligations with regard to the publication of the results of research. Authors have a duty to make publicly available the results of their research on human patients and are accountable for the completeness and accuracy of their reports. They should adhere to accepted guidelines for ethical reporting. Negative and inconclusive as well as positive results should be published or otherwise made publicly available. Sources of funding, institutional affiliations and conflicts of interest should be declared in the publication. Reports of research not in accordance with the principles of this Declaration should not be accepted for publication.

C. ADDITIONAL PRINCIPLES FOR MEDICAL RESEARCH COMBINED WITH MEDICAL CARE

1. The physician may combine medical research with medical care only to the extent that the research is justified by its potential preventive, diagnostic or therapeutic value and if the physician has good reason to believe that participation in the research study will not adversely affect the health of the patients who serve as research patients.
2. The benefits, risks, burdens and effectiveness of a new intervention must be tested against those of the best current proven intervention, except in the following circumstances:
 - a. The use of placebo, or no treatment, is acceptable in studies where no current proven intervention exists; or
 - b. Where for compelling and scientifically sound methodological reasons the use of placebo is necessary to determine the efficacy or safety of an intervention and the patients who receive placebo or no treatment will not be patient to any risk of serious or irreversible harm. Extreme care must be taken to avoid abuse of this option.
3. At the conclusion of the study, patients entered into the study are entitled to be informed about the outcome of the study and to share any benefits that result from it, for example, access to interventions identified as beneficial in the study or to other appropriate care or benefits.
4. The physician must fully inform the patient which aspects of the care are related to the research. The refusal of a patient to participate in a study or the patient's decision to withdraw from the study must never interfere with the patient-physician relationship.

In the treatment of a patient, where proven interventions do not exist or have been ineffective, the physician, after seeking expert advice, with informed consent from the patient or a legally authorized representative, may use an unproven intervention if in the physician's judgment it offers hope of saving life, re-establishing health or alleviating suffering. Where possible, this intervention should be made the object of research, designed to evaluate its safety and efficacy. In all cases, new information should be recorded and, where appropriate, made publicly available.

